#### **5.5.4 Selection and Timing of Dose for Each Subject**

Subjects should take study drug as outlined in Section [5.5.1](#).

On dosing days that occur on study visit days, subjects should follow the regular dosing schedule (refer to Section [5.3.2.1](#) regarding Week 1 and Week 2 visits).

Each subject's dosing schedule should be closely monitored by the site at each study visit by careful review of the subject's dosing diary. This will ensure that all subjects enrolled into the study maintain their original dosing schedule beginning with the first dose of study drug (Baseline/Day 1).

If a subject should forget to take their upadacitinib (or matching placebo) dose at their regularly scheduled dosing time, they should take the forgotten dose as soon as they remember the dose was missed as long as it is at least 10 hours before their next scheduled dose. If a subject only remembers the missed dose within 10 hours before next scheduled dose, the subject should skip the missed dose and take the next dose at the scheduled time.

If the subject experiences a study drug interruption > 7 consecutive days during Weeks 1 through 24 or > 30 consecutive days after Week 24, they should notify their study site physician, and the subject should be discontinued from the study.

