**5.4 Removal of Subjects from Therapy or Assessment****5.4.1 Discontinuation of Individual Subjects**

Subjects can request to be discontinued from participation in the study at any time for any reason, including but not limited to disease progression or lack of response to treatment. The Investigator may discontinue any subject's participation for any reason, including an AE, safety concerns, lack of efficacy, or failure to comply with the protocol. See Section 6.1.7 for toxicity management criteria.

Subjects will be withdrawn from the study immediately if any of the following occur:

- Clinically significant abnormal laboratory results or AEs, which rule out continuation of the study drug, as determined by the Investigator or the AbbVie Therapeutic Area Medical Director.
- Serious infections (e.g., sepsis) which cannot be adequately controlled within 2 weeks by anti-infective treatment or would put the subject at risk for continued participation in the trial as determined by the Investigator.
- The Investigator believes it is in the best interest of the subject.
- The subject requests withdrawal from the study.
- Inclusion or exclusion criteria violation was noted after the subject started study drug, when continuation of the study drug would place the subject at risk as determined by the AbbVie Therapeutic Area Medical Director.
- Introduction of prohibited medications or dosages when continuation of the study drug would place the subject at risk, as determined by the AbbVie Therapeutic Area Medical Director.
- Subject is non-compliant with TB prophylaxis (if applicable) or develops active TB at any time during the study.
- The subject becomes pregnant while on study drug.
- Malignancy, except for localized NMSC or carcinoma in situ of the cervix.
- Subject is significantly non-compliant with study procedures which would put the subject at risk for continued participation in the trial as determined by the Investigator.

- Subject develops a gastrointestinal perforation.
- Starting at Week 24, at least 20% improvement in BOTH TJC and SJC compared to baseline is required to remain in the study. Anyone who does not fulfill this criterion at 2 consecutive visits (starting at Week 24) must be discontinued from the study.

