The Investigator should contact the AbbVie TA MD if a subject experiences a study drug interruption > 7 consecutive days during Weeks 1 through 24 or > 30 consecutive days after Week 24 (other than for reasons listed in Section 6.1.7) to discuss the management of the subject and possible discontinuation from participation in the study.

If a subject prematurely discontinues study participation, the procedures outlined for the Premature Discontinuation visit (PD visit) should be completed as soon as possible, preferably within 2 weeks. In addition, if subject is willing, a 30-day follow-up visit/phone call after the last dose of study drug may be completed to ensure all treatment emergent AEs/SAEs have been resolved. Subjects who discontinue the study prematurely after randomization will not be replaced.

All attempts must be made to determine the date of the last study drug dose and the primary reason for discontinuation of study participation. The information will be recorded on the appropriate eCRF page. However, these procedures should not interfere with the initiation of any new treatments or therapeutic modalities that the Investigator feels are necessary to treat the subject's condition. Following discontinuation of study drug, the subject will be treated in accordance with the Investigator's best clinical judgment.

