**Table 8. Specific Toxicity Management Guidelines for Abnormal Laboratory Values (Continued)**

Laboratory Parameter	Toxicity Management Guideline
AST or ALT (continued)	
 
For subjects with HBc Ab+ (irrespective of HBs Ab status) and negative HBV DNA at screening who manifest an ALT > 5 × ULN OR ALT/AST > 3 × ULN and either a total bilirubin > 2 × ULN or INR > 1.5 OR ALT/AST > 3 × ULN along with clinical signs of possible hepatitis, HBV DNA by PCR testing should be performed within 1 week. A positive result for HBV DNA PCR testing in these subjects will require immediate interruption of study drug and a hepatologist consultation should occur within 1 week for recommendation regarding subsequent treatment.
 
 
For any confirmed ALT or AST elevations > 3 ULN, complete supplemental hepatic eCRF.

Serum Creatinine	
 
If serum creatinine is > 1.5 × baseline value and > ULN, repeat the test for serum creatinine (with subject in an euvolemic state) to confirm the results. If the results of the repeat testing still meet this criterion, then interrupt study drug and re-start study drug once serum creatinine returns to ≤ 1.5 × baseline value and ≤ ULN.
 
If confirmed serum creatinine ≥ 2 mg/dL, interrupt study drug and re-start study drug once serum creatinine returns to normal reference range or its baseline value.
 
 
For the above serum creatinine elevation scenarios, complete supplemental renal eCRF.

Creatine Phosphokinase	
 
For confirmed CPK value ≥ 4 × ULN, and there are no symptoms suggestive of myositis or rhabdomyolysis, the subjects may continue study drug at the investigator's discretion.
 
If CPK ≥ 4 × ULN accompanied by symptoms suggestive of myositis or rhabdomyolysis, interrupt study drug and contact the AbbVie TA MD.
 
 
For the above CPK elevation scenarios, complete supplemental CPK eCRF.

For allowed study drug interruption, the following rules apply:

### Period 1

- Allow study drug interruption up to 7 consecutive days for AEs and emergency surgery. Elective surgery will not be allowed during this 12 week period.

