**Period 2**

- Allow study drug interruption up to 7 consecutive days for AEs and emergency surgery during Week 16 to Week 24 in Period 2, and after Week 24 until Week 64/PD, up to 30 consecutive days of study drug interruption is allowed.
- If the subject undergoes elective surgery, the study drug should be interrupted 1 week prior to the planned surgery. Allow reintroduction of study drug once the physician has examined the surgical site and determined that it has healed and there is no sign of infection.
- If the subject must undergo emergency surgery, the study drug should be interrupted at the time of surgery. Allow reintroduction of study drug once the physician has examined the surgical site and determined that it has healed and there is no sign of infection.

The Investigator should contact the AbbVie TA MD if a subject experiences a study drug interruption > 7 consecutive days during Weeks 1 through 24 or > 30 consecutive days after Week 24 to discuss the management of the subject and possible discontinuation from participation in the study.

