6.4 Protocol Deviations

Protocol deviations are categorized as follows based on ICH deviation criteria:

- Those who entered the study even though they did not satisfy the entry criteria
- Those who developed withdrawal criteria during the study and were not withdrawn
- Those who received the wrong treatment or incorrect dose, and
- Those who received an excluded or prohibited concomitant medication.

The protocol deviations listed above will be summarized and listed by treatment group.

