9.1.2 Definition of Missing Data Imputation

Non-Responder Imputation (NRI) Approach

The NRI approach will categorize any subject who has missing value for categorical variables at a specific visit as non-responder for that visit. In addition, subjects who prematurely discontinue from study drug will be considered as non-responders for all subsequent visits after discontinuation.

Observed Cases (OC)

The OC analysis will not impute values for missing evaluations, and thus a subject who does not have an evaluation on a scheduled visit will be excluded from the OC analysis for that visit. In addition, the OC will not use values after premature discontinuation of study drug. This sensitivity analysis will only be applied to the analysis in Period 1.

As Observed (AO)

The AO analysis will not impute values for missing evaluations, and thus a subject who does not have an evaluation on a scheduled visit will be excluded from the AO analysis for that visit. Regardless of treatment switching or premature discontinuation of study drug, all observed data will be used in the analysis. The AO analysis will be applied to long-term efficacy analysis.

Mixed Effect Model Repeat Measurement (MMRM)

The repeated measure analysis will be conducted using mixed model including observed measurements at all visits. The mixed model includes the categorical fixed effects of treatment, visit and treatment-by-visit interaction, main stratification factors at randomization, and the continuous fixed covariates of baseline measurement. An unstructured variance covariance matrix will be used. The parameter estimations are based on the assumption of data being missing at random and using the method of restrictive maximum likelihood (REML). The missing at random assumption is considered reasonable given the high placebo response rate typically seen in RA trials. Additionally, in RA trials, the proportion of discontinuation is relatively small (10 – 15% only) and the rate of discontinuation due to lack of efficacy is generally low (< 5%).

Multiple Imputation (MI)

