- $ACR_{xx} = 0$ if TJC indicator = 0 OR SJC indicator = 0 OR at least 3 out of 5 components improvement indicators = 0.
- $ACR_{xx} = 1$ if TJC indicator = 1 AND SJC indicator = 1 AND at least 3 out of 5 components improvement indicators = 1.
- For all other cases, ACR_{xx} = missing since ACR_{xx} cannot be determined.

The following table illustrates examples for ACR calculations.

Example	TJC 68	SJC 66	Component 1	Component 2	Component 3	Component 4	Component 5	ACR20- Response?
A	1	1	1	1	1	.	.	Yes
B	1	0	1	1	1	1	1	No
C	.	0	No
D	1	.	1	1	1	1	1	.
E	1	1	0	0	0	1	1	No
F	.	.	0	0	0	.	.	No
G	1	1	1	1	0	0	.	.

Legend: 1 = \geq 20% improved compared to baseline; 0 = < 20% improved compared to baseline; " ." missing.

Windowing Rule for ACR Response Calculation:

- ACR component values will first be determined at each date within a visit window.
- ACR component values at each date will be combined to determine the observed ACR composite score at each date in each window.
- After this calculation, if multiple non-missing ACR composite scores are available within a given visit window, the non-missing ACR composite score

closest to the target day will be used. If two composite scores have the same distance from the target day, the later one will be used. The corresponding date will be used as the observed ACR response date in the derived efficacy dataset.

- If a non-missing ACR composite score is not available for any day within a given visit window, the windowed component values for that visit will be used to calculate the ACR composite score for that visit window (component value windowing follow the same rules as in steps described above). The date of observed ACR composite score will be determined by the first available ACR component date, in the order of TJC, SJC, Pain, PGA, PhGA, HAQ-DI, CRP/ESR, in the derived efficacy dataset.

When observed ACR xx response for a given visit is missing, imputation methods will be used to calculate "imputed" ACRxx response.

Non-Responder Imputation (NRI) for ACR response:

- Step 1: all missing components will be imputed using LOCF, and then the ACR composite score can be calculated.
- Step 2: if the ACR composite score cannot be determined by Step 1, the ACR composite score will be imputed as 0. In addition, subjects who prematurely discontinue from the study drug will be considered as non-responders (ACR = 0) for all subsequent visits after the discontinuation date.

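### Protocol 5.5.4 discontinues a subject after a long dosing interruption, where 5.4.1 and 6.1.7 call only for a discussion with the sponsor's medical director

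*Protocol*

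**What the plan says.** Three current sections of the protocol address the same event, a study-drug interruption of more than 7 days in a row up to Week 24 or more than 30 days in a row later.

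- **Protocol 5.5.4**, on selection and timing of dose, ends with this instruction for affected subjects: "they should notify their study site physician, and the subject should be discontinued from the study". It mentions no contact with the sponsor and no exception.
- **Protocol 5.4.1**, on discontinuation of individual subjects, has the investigator contact the sponsor's medical director: "other than for reasons listed in Section 6.1.7) to discuss the management of the subject and possible discontinuation". The same section opens its mandatory list with "Subjects will be withdrawn from the study immediately if any of the following occur". Drug interruption is not on that list.
- **Protocol 6.1.7**, on toxicity management, closes with the same contact rule at the same thresholds: "consecutive days after Week 24 to discuss the management of the subject and possible discontinuation from participation in the study". For Period 1 it also says "Allow study drug interruption up to 7 consecutive days for AEs and emergency surgery".

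The analysis side is in the SAP. Section 9.1.2 says that under NRI "subjects who prematurely discontinue from study drug will be considered as non-responders for all subsequent visits after discontinuation". Section 9.4.1 repeats this for the ACR endpoints: "subjects who prematurely discontinue from the study drug will be considered as non-responders (ACR = 0) for all subsequent visits after the discontinuation date".

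**The concern.** One trigger carries two different instructions. Under 5.5.4 the subject leaves the study. Under 5.4.1 and 6.1.7 the investigator has a conversation, after which the subject may leave or stay. No sentence says which section prevails, so two sites could handle identical subjects differently.

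Two things are at stake. A subject could lose access to treatment under a rule that the sponsor appears to have given up. In Period 1, the choice of section can also change how that subject is scored on the primary endpoint.

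**Working it through.** The check is mainly a comparison of texts, followed by one piece of arithmetic for scale.

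**Step 1: the trigger and the action.**

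| Section | Trigger | Action |
|---|---|---|
| 5.5.4 | >7 days up to Week 24; >30 days after | Subject tells the site physician and is discontinued |
| 5.4.1 | the same, for reasons outside 6.1.7 | Investigator contacts the medical director; discontinuation possible |
| 6.1.7, closing paragraph | the same | Investigator contacts the medical director; discontinuation possible |

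The thresholds match exactly. Only the action differs.

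**Step 2: which rule is intended.** The section that governs discontinuation leaves interruption off its mandatory list and places the contact rule directly after it. Section 6.1.7 agrees. The list of changes in Appendix P, used here only as evidence of intent, shows interruption being taken out of the mandatory list in 5.4.1 and the contact paragraph being added to 6.1.7. It has no entry for 5.5.4.

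Section 6.1.7 also provides for pauses that 5.5.4 would not tolerate. For elective surgery in Period 2, drug stops one week beforehand and restarts only after the site has healed, which must exceed 7 days. Before Week 24, 5.5.4 would remove a subject who followed that instruction.

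**Step 3: the effect in Period 1.** Take a subject who misses 8 days in a row with no adverse event or surgery.

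- Under 5.5.4 the subject is discontinued, and NRI sets ACR20 to non-response at Week 12.
- Under 5.4.1 the medical director is contacted. If the subject is retained, Week 12 is scored on the subject's own data.

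The same divergence arises when an interruption for an adverse event or emergency surgery runs past the 7 days that 6.1.7 allows. The closing paragraph of 6.1.7 then asks for contact, while 5.5.4 says discontinue.

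**Step 4: the size of one case.**

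- Inputs: 161 subjects planned per arm (Protocol 5.1 and 8.3). Placebo ACR20 rate 36.7% and difference 21.7 points (Protocol 8.2, SAP 4.3), so the active rate is 36.7 + 21.7 = 58.4%.
- One responder rescored as a non-responder: 1/161 = 0.0062, or 0.62 points in that arm.
- Relative to the planned difference: 0.62/21.7 = 0.029, or about 3% of it.

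The direction depends on the arm. A rescored responder on upadacitinib narrows the difference, and one on placebo widens it. The documents give neither the frequency of such interruptions nor their split between arms, so the calculation stops here.

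**The case against.** The strongest reply is that the protocol resolves this in practice. Section 5.4.1 is the section on discontinuation, two of the three sections agree, and 5.5.4 is a dosing section whose sentence is addressed to the subject. It says the subject should be discontinued, whereas firm rules elsewhere, such as those for gastrointestinal perforation or failure of the 20% joint criterion, use must. Much of this stands. The intended rule is clear, and the defect is a missed conforming edit rather than an open choice.

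It does not clear 5.5.4. The contact rule is also phrased with should, so the verb does not rank one instruction above the other. Nor can 5.5.4 be limited to forgotten doses: its sentence covers any interruption, and forgotten doses fall outside the reasons in 6.1.7, so 5.4.1 would call for contact there too.

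A reader might infer three stronger points, which the documents do not support.

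- **That 5.4.1 and 6.1.7 contradict each other**, because only 5.4.1 exempts the reasons in 6.1.7. The two can be reconciled: 5.4.1 covers interruptions outside 6.1.7, the closing paragraph of 6.1.7 covers its own, and contact is required in both cases.
- **That a retained subject becomes a deviation and drops out of the Per Protocol set.** SAP 6.4 counts "Those who developed withdrawal criteria during the study and were not withdrawn", but the withdrawal list in 5.4.1 omits interruption. Under SAP 5.1, major deviations are identified before database lock, and SAP 9.2.2 makes the Per Protocol analysis supportive only.
- **That power falls below the planned 90%.** The sample size already allows for 10% dropout, and subjects removed for interruption are dropouts. The full analysis set with NRI keeps every dosed subject in the denominator. Adding assumed removals to a sample already reduced for dropout would count the same losses twice, using rates that the documents do not give.

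**Conclusion.** The inconsistency holds in current text and is confined to the last sentence of Protocol 5.5.4. It is minor. It reaches the primary result only if three things coincide: an interruption of more than 7 days arises before Week 12, the site applies 5.5.4 rather than 5.4.1 or 6.1.7, and the subject would otherwise have been an ACR20 responder at Week 12. Each such subject costs the arm 0.62 points, assuming that all 161 planned subjects per arm are dosed. The total effect is unknown and probably small. In Period 2 the effect is on subject handling and not on inference, because SAP 9.1.1 makes long-term efficacy descriptive with no testing.

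**What to change.** In the last sentence of Protocol 5.5.4, keep the subject's duty to tell the site physician. Replace the clause that discontinues the subject with the instruction already in 5.4.1 and 6.1.7: the investigator should contact the sponsor's medical director to discuss the subject's management and possible discontinuation from the study. No change is needed to 5.4.1, 6.1.7 or the SAP. The cost is a one-sentence edit and a short clarification to sites, with no new data and no additional patients.

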### **5.5.5      Blinding**

#### **5.5.5.1      Blinding of Investigational Product**

Period 1 will be double blinded. All AbbVie personnel with direct oversight of the conduct and management of the trial (with the exception of AbbVie Drug Supply Management Team), the Investigator, study site personnel, and the subject will remain blinded to each subject's treatment during this period.

In order to maintain the blind, the upadacitinib tablets and placebo tablets provided for the study will be identical in appearance. The IRT will provide access to unblinded subject treatment information in the case of medical emergency.

In the event of a medical situation that requires unblinding of the study drug assignment, the Investigator is requested to contact the AbbVie Therapeutic Area Medical Director prior to breaking the blind. However, if an urgent therapeutic intervention is necessary which warrants breaking the blind prior to contacting the AbbVie Therapeutic Area Medical Director, the Investigator can directly access the IRT system to break the blind without AbbVie notification or agreement. Unblinding is available in the IRT system via the Unblind Subject transaction, which is available only to the Investigator. If the IRT system is unavailable, unblinding may occur by contacting EndPoint technical support via either phone (preferred) or email ([contact]). For country-specific phone numbers, please see the following website: <http://www.endpointclinical.com/help-desk/>. In the event that the blind is broken before notification to the AbbVie Therapeutic Area Medical Director, AbbVie requests that the AbbVie Therapeutic Area Medical Director be notified within 24 hours of the blind being broken. The date and reason that the blind was broken must be conveyed to AbbVie and recorded on the appropriate eCRF.

The primary analysis will be conducted after all subjects have completed Period 1 (Week 12) or have prematurely discontinued prior to Week 12. Study sites and subjects will remain blinded to the treatment assignment in Period 1 for the duration of the study.

#### **5.5.5.2 Blinding of Data for Data Monitoring Committee**

An external Data Monitoring Committee (DMC) comprised of persons independent of AbbVie and with relevant expertise in their field will review unblinded safety data from the ongoing study. The primary responsibility of the DMC will be to protect the safety of the subjects participating in this study.

A separate DMC charter will be prepared outside of the protocol and will describe the roles and responsibilities of the DMC members, frequency of data reviews, and relevant safety data to be assessed.

Communications from the DMC to the Study Teams will not contain information that could potentially unblind the team to subject treatment assignments.

